## Study Overview

A cluster randomized controlled trial of 18 school based health centers (SBHCs) with 1,360 Latina adolescents evaluated the extent to which the app: (1) supports adolescents in making decisions about an effective method of contraception; (2) improves the effectiveness and efficiency of the clinical encounter; and (3) reduces the incidence of unprotected sexual intercourse among Latina adolescent girls over time. The long term goal of the intervention is to reduce health disparities in unintended pregnancy rates for Latina adolescents. Clinics provided all adolescent girls with an iPad. The iPad assessed eligibility and obtained consent. Participants in the nine intervention clinics received the app and those from nine control clinics received standard of care sexual health questions. In addition to the baseline, pre-visit questionnaire, participants were asked to complete follow-up surveys within 48-hours, 3 and 6 months after the visit. Differences in adolescents' contraceptive knowledge, attitudes, self-efficacy and use over the 6-month follow up was assessed by generalized mixed effects models that to account for repeated measures, a time effect, the time by group interaction, and demographic covariates.

## Study Setting

Our study took place in Los Angeles County which holds the second largest school district in the United States. It is an ideal setting to conduct this cluster randomized control trial as it has a large number of SBHCs, serves a large proportion of Latina adolescents and has high rates of unintended pregnancies and sexually transmitted infections (STIs) (reflecting unprotected sex).i,ii In addition, these sites expressed a willingness and commitment to participating in a rigorous, randomized control trial.

## Participants

Participant recruitment began in August 2016 and continued through May 2018. All adolescent girls ages 14- 18 years who visited any of the participating SBHCs, regardless of reason for visit, were invited to use an iPad with the web application. The computer assessed eligibility of the teens using an online screener built in to the app. The inclusions criteria for the study is outlined below.

### Inclusion criteria

Adolescents were eligible to participate in the study if they met the following criteria:

- Female
- Aged 14–18 years
- Hispanic/Latina
- Had an appointment at a participating SBHC
- English-speaking or Spanish-speaking

- Sexually active (have had sexual intercourse)
- Not currently pregnant or not sure that they are pregnant (adolescents with a previous pregnancy and who are not currently pregnant were eligible)
- Not using an LARC method of contraception at the time of the screening.

#### Exclusion criteria

Adolescents were not eligible to participate in the study if they were:

- Not biologically female
- 13 years or younger or 19 years or older
- Did not identify as Hispanic/ Latina
- Used the app outside of a participating SBHC appointment
- Not sexually active
- Pregnant at the time of screening
- Using a LARC method of contraception at the time of screening
- Did not complete the intervention or baseline questionnaire

SBHCs were randomly assigned, at equal chance, to either the intervention (*Health-E You/Salud iTu* app) or control group (standard of care, no app). This design allows our analyses to isolate the effect of the app and determine whether the app increases adolescent sexual health and contraceptive knowledge, self-efficacy in selecting an effective method, satisfaction with the visit and contraceptive use and adherence over time.

Clinics were randomized to either control or intervention group using computer-generated random number assignment. Following randomization, our local partners from The Los Angeles Trust for Children’s Health (LA Trust) notified the SBHCs of their assignment and provided the necessary training around the study aims, use of the iPad and integration into the unique workflow at each SBHC (determined in partnership with our community outreach staff and clinic staff, providers and managers). The LA Trust also provided technical support to ensure that all sites had a reliable internet connection to be able to use the app as intended and to securely transmit data gathered from the app to the University of California, San Francisco (UCSF).

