### Data Collection and Sources

Follow-up procedures are designed to maximize participant retention over time and minimize bias due to attrition. Youth were informed that they would receive a financial incentive of up to US\$70 for completing all follow-up surveys. The following is the incentive structure:

- US\$10 for completing the baseline information and immediate follow-up survey,
- US\$20 for completing the 3-month follow-up assessment,
- US\$20 for completing the 6-month follow-up,
- US\$20 bonus for completing all surveys.

Participants were enrolled in the study for a total of six months (with one additional month to complete follow-up surveys) following their initial clinic visit, where they interacted with our Health-E You app or completed the baseline survey. We also collected the youth's preferred method of contact (e-mail and, or cell phone) to provide them with their follow-up surveys and e-gift cards. We also explained that their participation was completely confidential.

Each participant was sent their survey link by email and / or text. Non-respondents received up to three reminders to complete their follow-up survey. Those who provided phone information were also contacted by phone to either complete the survey immediately by phone or to have the link resent to them. Participants had one week to complete the immediate follow-up survey and up to 30 days to complete the 3 and 6 month follow-up surveys. In addition, we designed our follow-up surveys so that we can capture data from participants who did not respond to previous follow-up surveys. This was an additional strategy to reduce our overall attrition.

We were unable to ascertain exactly why individual participants were lost to follow-up because of the remote nature of the study. However, while conducting follow-up procedures, our team noted that many phone numbers had changed or were no longer valid, or e-mails bounced back. This population is of Latina background and we heard two issues that impacted the study. One is that participants return to visit family members in Mexico for extended time periods. Another was concerns over immigration “crackdowns” and were worried that sharing contact information may put family members and/or friends at risk – regardless of the participant’s immigration status.

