#### Handling Missing Data

Since each assessment involves a relatively brief self-administered instrument, the amount of missing data due to failure to provide data was minimal. The largest source of missing data was participant dropout. Of the 1360 participants in the study cohort 778 (57.2%) responded to the 48-hour survey, 681 (50.1%) responded to the 3-month survey, 676 (49.7%) responded to the 6-month survey, and 575 (42.3%) responded to both the 3-month survey and the 6-month survey.

Consequently, to minimize bias due to attrition, we employed multiple imputation so that every regression model could be fit to all available data while invoking the mild assumption that the data were missing at random. Imputation was performed on the data in wide format (one record per case) to correctly account for dependence in multiple observations per case. In models testing a time by treatment group, missing data were imputed separately for intervention cases and control cases. Imputation models contained all variables in the analysis model (including the outcome), baseline variables identified as correlates of retention, and indicator variables representing recruitment site (SBHC).

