#### Heterogeneity of Treatment Effects

A concern in any cluster randomized control trial is whether or not the treatment effect is robust across sites. However, small per site sample sizes preclude direct comparisons between sites because of a lack of statistical power. We investigated the sensitivity of the intervention effect to recruitment site (SBHC) in the two primary outcomes where we assessed changes from baseline to

3-month and 6-month follow-up: contraception use self-efficacy (Aim 1c, Primary Outcome 2) and non-barrier contraception use (Aim 3b, Primary Outcome 3). For both outcomes, the time by treatment group interaction served as the direct test of the intervention effect. With three time points and two treatment groups, the interaction was represented by two parameter estimates. The sensitivity analysis employed a jack-knife technique where the analysis is repeated but with participants from one intervention SBHC removed from the analysis. Since there were 9 SBHCs randomly assigned to each treatment group, the jack-knife technique required 9 new models be assessed.

Table 2 reports the point estimate, 95% confidence interval, and p-value for each parameter obtained from the mixed effects regression analysis model including all 9 intervention SBHCs plus the range of parameter estimates and p-values obtained from the jack-knife analyses (models that included only 8 intervention SBHCs).

**Table 2. Parameter Estimates from Sensitivity Analyses Compared to Parameter Estimates from Analytic Models for Two Primary Outcomes**

Outcome	Interaction Parameter	Estimate	Analytic Model		Sensitivity Analyses	
			95% CI	p-value	Estimates	p-value
Contraception Use Self-efficacy	1	0.816	-0.482, 2.115	.218	0.477-1.086	.098-.408
	2	1.576	0.377, 2.774	.010	1.269-1.729	.006-.037
Non-barrier Contraception	1	1.190	0.043, 2.338	.042	1.128-1.350	.024-.063
	2	1.711	0.529, 2.544	.005	1.511-1.936	.003-.012

For both outcomes, the data suggest the intervention effect is not sensitive to recruitment site (SBHC).

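### Removing girls who did not complete the app or the baseline questions is a post-randomisation exclusion that falls unequally on the arms, so the analysed cohort is not intention-to-treat; direction and size of bias are unknown

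*Combined protocol and SAP*

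**What the plan says.** Allocation is by clinic: "SBHCs were randomly assigned, at equal chance, to either the intervention" or control group (text under Exclusion criteria). Heterogeneity of Treatment Effects confirms the numbers: "Since there were 9 SBHCs randomly assigned to each treatment group". After randomisation, the local partner "notified the SBHCs of their assignment and provided the necessary training around the study aims". Girls were then screened and consented on an iPad at a clinic visit (Study Overview; Participants).

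The last item of the exclusion list removes a girl who "Did not complete the intervention or baseline questionnaire".

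The iPad task differs by arm. Study Overview states: "Participants in the nine intervention clinics received the app and those from nine control clinics received standard of care sexual health questions". Data Collection and Sources describes the first visit as the one "where they interacted with our Health-E You app or completed the baseline survey". The analytical section adds that contraceptive knowledge was tested just before and just after app use, in the intervention group only.

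Handling Missing Data starts from the filtered cohort: "Of the 1360 participants in the study cohort 778 (57.2%) responded to the 48-hour survey". Its remedy is aimed at later dropout: "to minimize bias due to attrition, we employed multiple imputation so that every regression model could be fit to all available data". The plan defines no intention-to-treat set and does not say how many girls in each arm were removed for not completing.

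**The concern.** Whether a girl completes is known only after her clinic has been allocated and she has begun the task her arm assigns. Completion is thus a post-randomisation event that the arm itself can influence, and it decides who is analysed. If girls who stop the app part-way are less engaged or short of time, removing them from one arm has two effects. It leaves a more engaged intervention group, and it takes out girls who received little of the intervention and would have diluted its effect. Either would weaken the comparability that cluster randomisation is meant to give, and the plan has no analysis that would reveal it.

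**Working it through.** **1. Who can be removed, and for what.** In the app arm, a girl can fail on the baseline questionnaire or on the app. In the control arm, she can fail only on the baseline questions. Both arms have a filter; the app arm has one more way to fail it.

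**2. Whether the plan restores the removed girls.** The imputation fills in missing follow-up within the 1,360. The jack-knife leaves out one intervention clinic at a time from that same cohort. Neither covers a girl who never entered it.

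**3. Which outcomes are exposed (Analytical and statistical approaches).**
- Discussing birth control and receiving a method at the visit: logistic regression on arm, age, visit purpose and recent sexual activity. There is no baseline value, so a selected app arm feeds directly into the arm effect, apart from what these covariates explain.
- Self-efficacy, and non-barrier use at 3 and 6 months: tested by the time-by-group interaction with baseline as a time point. Stable differences between completers and non-completers cancel. What remains is removed dilution and any difference in change over time.

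**4. The plan's own figure.** Table 1, visit row: N = 505, control 39%, 18 clinics, ICC .01, power .80, alpha .05 taken as two-sided.
- Cluster size m = 505/18 = 28.1; design effect = 1 + 27.1 × .01 = 1.271.
- Effective n per arm = 252.5/1.271 = 198.7.
- h = (1.960 + 0.842) × √(2/198.7) = .281, or 14.0 points. Table 1 states .282 and +14.

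The other cells reproduce to the stated points in the same way. Table 1 runs from 12 points (6 months, ICC .01) to 23 points (visit, ICC .09).

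**5. Size for a single-time proportion (assumed values).** Let f be the share of app-arm girls removed, and pC and pN the outcome rates of completers and non-completers. The rate among all girls is (1 − f)pC + f·pN, so the completers-only rate exceeds it by f(pC − pN). If control removals are ignored:

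| Share removed f | Gap pC − pN | Shift |
|---|---|---|
| 5% | 10 to 30 points | +0.5 to +1.5 |
| 10% | 20 points | +2 |
| 20% | 30 points | +6 |
| 30% | 10 to 30 points | +3 to +9 |
| 20% | −20 points | −4 |

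Control removals act in the opposite direction: the net shift is f(app) × gap(app) − f(control) × gap(control). For example, 10% against 5%, both with a 20-point gap, gives 2 − 1 = 1 point.

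**6. Effect on error at the visit (ICC .01, no true effect, no covariate adjustment).**
- Shift of 2 points: SE = √[(.39 × .61 + .41 × .59)/198.7] = .0491, and .02/.0491 = 0.41. Two-sided type I error = Φ(0.41 − 1.96) + Φ(−0.41 − 1.96), about 7%.
- Shift of 6 points: SE = √[(.39 × .61 + .45 × .55)/198.7] = .0494, and .06/.0494 = 1.21. Type I error is about 23%.

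**7. Dilution in the interaction models (Table 2, rough).** If removed girls gain nothing and the SE stays fixed, restoring them multiplies the estimate by (1 − f). The lower 95% limit reaches zero at f = lower limit / estimate.
- Non-barrier use, parameter 1: 0.043/1.190 = 3.6%.
- Self-efficacy, parameter 2: 0.377/1.576 = 24%.
- Non-barrier use, parameter 2: 0.529/1.711 = 31%. The printed interval, 0.529 to 2.544, is not centred on 1.711; the lower limit agrees with p = .005.

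Table 2 does not say which follow-up each parameter represents.

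**The case against.** Four points on the other side carry weight.

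- A reader might infer that only the app arm can fail this filter. The documents do not support that: the item also names the baseline questionnaire, which control girls can leave unfinished. It could even be read as one entry questionnaire per arm, and Data Collection and Sources fits that reading. The required session would still differ by arm, and only app-arm girls had knowledge tests around it, so the inequality stands. How much longer the app session took is not stated.
- A reader might infer that the rule favours the app. The documents give neither the number of non-completers nor their outcomes. A girl already using a method, or called in early for a contraceptive visit, could also leave the app unfinished, and the sign would reverse.
- A reader might infer that every primary outcome is equally compromised. The interaction tests cancel stable differences, so they are better protected than the visit outcomes. Method receipt is itself primary under Study Outcomes (Aim 3a) but Secondary Outcome 3 in the analytical section.
- The percentage-point arithmetic does not carry over to a log-odds interaction or a 0–30 score, and setting 6 points against only the 12-point cell would flatter the concern. The 3.6% figure mainly shows that p = .042 is fragile.

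None of this supplies the missing counts or an analysis that covers the removed girls.

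**Conclusion.** The concern holds in a limited form. A stated rule selects the analysed girls on a post-randomisation event that depends on arm; the resulting 1,360 are not an intention-to-treat set; and no planned analysis repairs or probes this. Bias towards the app is plausible, but direction and size cannot be established from the documents.

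Under the assumed values, the shift in a visit proportion runs from negligible to several points. The 6-point case compares with 14, 19 or 23 detectable points in the visit row of Table 1, that is 43%, 32% or 26% of them. These figures rest on assumed removal shares and gaps, with control removals ignored. For the repeated outcomes the open question is removed dilution: small removals would matter for the p = .042 result, and only large ones for the p = .010 and p = .005 results.

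**What to change.** 1. Remove non-completion of the intervention as an exclusion. Define the primary analysis set as all girls who passed the screener and consented, by clinic allocation, with the same rule in both arms.
2. Report the number removed in each arm, separately for the app and for the baseline questionnaire. This comes first, because very small counts would largely settle the matter.
3. Include non-completers from both arms with whatever data were captured. Add a sensitivity analysis that imputes app-arm non-completers from the control-arm model: the planned imputation for the interaction models is run separately by arm and would credit these girls with the app effect.
4. Present the completers-only result as supportive.
5. Where nothing was captured for the removed girls, give the counts and a range of assumed outcomes, and limit the conclusion to girls who completed the session. Follow-up ended in December 2018, so unmeasured outcomes cannot be recovered, and the documents do not say what partial records were kept.

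The cost is modest extra analysis, reliance on an imputation assumption that the data cannot verify, and possibly a less favourable estimate.

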#### Study Outcomes

The outcomes for this study were developed in collaboration with our community, clinic and adolescent partners to address three main questions:

- 1) How well does the patient-centered, interactive, individually tailored *Health-E You* app engage and support Latina adolescents in understanding their risk of an unintended pregnancy and in making decisions in selecting among effective contraceptive options that can reduce their risk?
- 2) To what extent does the app improve adolescents' and clinicians' perception of the quality and efficiency of the visit?
- 3) How well does the app improve, sexually active Latina adolescents use of and adherence to effective contraceptives over time?

From these questions, we developed the specific study aims and corresponding outcome measures. The following is a description of each outcome measure for each study aim, the type of outcome (primary or secondary), the rationale for the outcome measure and the purpose for the measure.

**Aim 1: Examine the extent to which the Health-E You contraceptive app supports adolescents in making decisions about an effective method of contraception.**

Aim 1a) increase adolescents' knowledge of sexual health and contraceptive options

Outcome Measure: Knowledge was a secondary measure that was assessed with a 7-item scale that used a true/false format (scores range 0-7). A higher score indicates more knowledge. The items are: 1) Birth control pills do not reduce the risk of getting a sexually transmitted disease (STD); 2) As long as the male partner pulls out before he ejaculates (cums), the female will not get pregnant; 3) Weight gain is a common side effect of most birth control methods, especially for the Intra-Uterine Device (IUD); 4) Birth control pills begin working as soon as you start taking them; 5) Decreased menstrual bleeding from using IUDs does not cause health problems later on; 6) Long-acting contraception methods, like the IUD and implant, can make it more difficult to become pregnant in the future; 7) The IUD is easy for a medical provider to insert and remove.

Rationale: Knowledge is an important component of the theoretical framework of the intervention aimed to change behavior. Youth indicated that misconceptions about contraception contributed to their selecting less effective methods. Youth informed content of app and corresponding knowledge items to improve the ability of the app to address common contraception misconceptions and empower youth to be more informed about their options.

Purpose: Information provided on the app was designed to increase knowledge in these key areas via a repeated, self-administered survey immediately before and again after using the app.

Aim 1b) increase the proportion of adolescents who report being prepared to select an effective form of contraception; and

Outcome Measures: Patient Activation/Readiness was measured with the following items: “The App helped me choose a method of birth control” and “The App gave me useful information about birth control”. Likert scale (options 1= strongly disagree to 5=strongly agree) which was then dichotomized into agrees versus neutral/disagrees.

Rationale: The app was designed to support adolescents in selecting a method that was a “good fit” based on their attitudes, goals, experiences and lifestyle considerations.

Purpose: To examine adolescent’s perspective on the value of the app in helping them become educated about birth control and support them in choosing a contraceptive method.

Aim 1c) increase adolescents’ self-efficacy to select and use an effective contraceptive method.

Outcome Measure: Contraception Use Self-efficacy. This primary outcome measure was based on a 3-item attitudinal scale to assess perceived confidence to choose and use contraception was self-administered via online survey. Each item scored on a 0-10 scale (0=not at all confident to 10=completely confident scale). Scale score is the sum of 3 items (range 0 – 30); higher score= greater self-efficacy. The questions were “How confident are you that you”.... 1) “can talk to your doctor about what birth control method(s) to use?” 2) “Can use birth control correctly so you do not get pregnant?” 3) “Have the information you need to choose the most appropriate birth control method for you?” It compares change in Intervention vs controls over time from baseline to 48-hour, 3-and 6 month follow-ups. Cronbach’s alpha ranged from .74 to = .80.

Rationale: Self-efficacy is a central aspect of the theoretical model predicting behavior change for the intervention. The purpose was to assess the effect of using the app at their health care visit on the self-confidence to choose and use contraception.

Purpose: To assess the effectiveness of the app on improving contraceptive knowledge so that youth would be able to make more informed decisions when selecting a method.

**Aim 2: Evaluate the efficacy of the Health-E You contraceptive app on its ability to improve the effectiveness and efficiency of the clinical encounter.**

2a) improve adolescents' and clinicians' perception of the quality and efficiency of the visit

Outcome Measures: App's Impact on Visit Quality was measured with the following items to capture the adolescents' perspectives: "The App improved the quality of my health care visit with my provider" "I liked the look/format of the Health-E You App", "I understood the information on the App.", "It was difficult to move through the App", "I experienced information overload using the App", "I would recommend this App to a friend", "I liked the video(s) of the health care provider", and "I liked the videos of teens talking about birth control". Likert scale (options 1=strongly disagree to 5=strongly agree); then dichotomized into agrees versus neutral/disagrees.

The following items captured the providers' perspectives: Provider Perceptions of App's Impact was assessed with the following items: "Helps engage teens in the contraceptive decision making process"; "Helps me provide a more individually-tailored discussion around contraceptive options"; "Helps me integrate reproductive health into all visit types (non-reproductive related health visits)", "Makes my clinic schedule run behind" and time spent on providing contraceptive care as measured by the following questions: "How much time did you spend providing basic contraceptive information", "How much time did you spend screening for potential medical contraindications for contraception" and How much time did you spend identifying what contraceptive method(s) would be the best fit for your patient?" Time to conduct activities was rated on a 5-point scale (1=did not spend any time to 5=a lot of time). Items were scored using a Likert scale (1=strongly disagree to 5=strongly agree); then dichotomized into agrees versus neutral/disagrees.

*Rationale:* The perceptions of both adolescents and providers are key in assessing the utility of the app on clinical practice. Provider stakeholders stated that in order for health technologies to be adopted into clinical practice they should support them in delivering clinical care which makes the visit more efficient and effective. Similarly, adolescents wanted the technology to be of value for their visit to enhance engagement, satisfaction and utility of the app. These measures help identify the benefits of implementing the app within clinics. These questions provide important information on the acceptability, feasibility, and value of implementing the App into clinical practice from both the provider and patient perspectives.

*Purpose:* To assess provider and adolescents ratings of how the app improved the effectiveness of the visit; providers' ability to provide more tailored discussion of contraception options during their clinic visits; adolescents' engagement in decision making from the provider perspective; the extent to which the app improved their ability to integrate reproductive health into all visit types; and the impact on timing/patient flow.

2b) increase the proportion of visits where adolescents and clinicians discussed contraception

*Outcome Measures:* Percentage of Adolescent Participants Who Report Discussing Birth Control with Health Care Provider at Visit. This was a secondary outcome measure that was asked of adolescents at the 48-hour follow up. Participants responded to the single item- "At your visit, did you discuss birth control with your health care provider?" via a self-administered survey and was a dichotomous yes-no measure.

*Rationale:* Provider discussion on birth control at the health care visit is a central component of the Health-E You clinical intervention. The app was designed as a contraception decision support tool aimed to facilitate communication about sexual health between adolescents and their provider. Thus, this question aims to gather information about how the app influenced patient-provider communication at the visit. Activating/empowering patients to seek the care they need is an important component of patient-centered contraceptive care.

Purpose: To examine the impact the app had on improving the proportion of adolescent and providers who discussed birth control at the visit by comparing differences in the Intervention and Control arms.

**Aim 3: Evaluate the effectiveness of the Health-E You contraceptive app to reduce the incidence of unprotected sexual intercourse (and associated unintended pregnancies) among Latina adolescent girls.**

3a) increase the proportion of sexually active adolescents who receive an effective contraceptive at their clinic visit

Outcome Measure: The primary outcome is the proportion of adolescent participants who report receipt of a non-barrier contraceptive method at their visit, a prescription for contraception or a follow-up appointment/referral for contraception. This was assessed at the 48-hour follow-up survey for both intervention and controls. Participants responded to the query of “Which of the following happened at this visit” (recent visit with your health care provider in which you used the Health-E You App via a self-administered survey at the 48-hour follow up): 1) Received birth control; 2) Made an appointment to receive contraception in the future; 3) Received prescription of hormonal contraception; 4) Did not receive a birth control prescription, referral or actual method.

Rationale: Receipt of effective non-barrier contraceptive methods is a central component reflecting the efficacy of the App to improve effective contraceptive use in this population. This measure helps to identify what happened during the health care visit, and to see if the Health-E You App improved the youth’s receipt of contraceptive services during their clinical visit.

Purpose: To assess the effectiveness of the app in improving the proportion of adolescents who receive contraception at their visit where they used the app.

3b) increase the proportion of sexually active adolescents who adhere to an effective contraceptive method over time -- at three and six months after their clinic visit.

Outcome Measure: This primary outcome measure was: self-reported use of non-barrier contraception in the prior 3 Months (along with type of contraceptive) assessed at baseline, 48 hour, 3- and 6 month follow-ups. Contraceptive methods were

dichotomized into non-barrier methods versus other methods/nothing used. In addition, change in contraceptive method efficacy was tracked over time. The list of methods included the following: 1) shot; 2) birth control pills; 3) patch; 4) ring; 4) male condoms; 5) female condoms; 6) pull-out/withdrawal; 7) rhythm/calendar; and 8) Other. Non-barrier contraception are categorized by tiers of effectiveness (CDC, WHO). The continuum of effectiveness of methods starting with least effective was coded as follows: (1) using nothing; (2) birth control pills, the patch, or the ring; (3) the shot; (4) IUD or Implant. IUD and implant were not included in the baseline list because adolescents using either were not eligible to participate; however they were listed for the 3- and 6- month follow-ups.

*Rationale:* This measure was used to assess the type of contraception used at each time point in order to understand the extent to which the app helped to support youth in selecting a more effective method of contraception to achieve their self-reported goal of avoiding a pregnancy.

*Purpose:* There were two purposes of this measure: 1) to examine differences in non-barrier contraceptive use between app users and controls over time (baseline, 3- and 6-month follow-up) and 2) it also was used to assess changes in contraceptive use over time to see if the app increased the arm (app users) use of more effective methods compared to controls.

